#### **11.3.4.    Unscheduled Visits**

If a subject has an unscheduled assessment then this data will be slotted to the closest adjacent scheduled visit within the appropriate reporting period (Parts A/B, Part C or Part D) where the endpoint data was scheduled to be collected according to the Time and Events schedule ([Appendix 2: Schedule of Activities](#)) unless data are already recorded at that visit. If an unscheduled visit occurred between two scheduled visits for which data has been reported, then the data from the unscheduled visit will remain in the unscheduled visit and will not be included in any by visit summary tables; it will however be included in relevant summaries of any time on-treatment data and listings.

### 11.3.5. Definitions of Assessment Windows for Analyses

The following assessments will be collected on a daily basis using an eDiary device: morning peak flow, usage of rescue medication (i.e. salbutamol/albutamol), asthma symptom score, frequency of awakening due to asthma symptoms requiring use of rescue medication and time missed from work/school. Part C data will be summarised in 4-weekly periods relative to the first Part C dose, as shown in the below table.

Domain	Parameter	Analysis Window 		Analysis Timepoint
		Beginning Timepoint	Ending Timepoint	
eDiary Data	morning peak flow, usage of rescue medication (i.e. salbutamol/albuterol), asthma symptom score, frequency of awakening due to asthma symptoms and time missed from work/school	6 days prior to day of first dose	Date of first dose	Baseline
		Day after day of first dose	28 days after day of first dose	Week 0-4
		29 days after day of first dose	56 days after day of first dose	Week 4-8
		57 days after day of first dose	84 days after day of first dose	Week 8-12
		85 days after day of first dose	112 days after day of first dose	Week 12-16
		113 days after day of first dose	140 days after day of first dose	Week 16-20
		141 days after day of first dose	168 days after day of first dose	Week 20-24
		169 days after day of first dose	196 days after day of first dose	Week 24-28
		197 days after day of first dose	224 days after day of first dose	Week 28-32
		225 days after day of first dose	252 days after day of first dose	Week 32-36
		253 days after day of first dose	280 days after day of first dose	Week 36-40
		281 days after day of first dose	308 days after day of first dose	Week 40-44
		309 days after day of first dose	336 days after day of first dose	Week 44-48
337 days after day of first dose	Week 52 visit date (or 364 days after day of first dose, if earlier)	Week 48-52		

- [1] Only non-missing eDiary measurements will be summarised in 4-weekly windows, see Section 11.7.2 for further details.
- [2] Day of first dose within this table referring to first dose of double-blind IP at visit C1. For subjects analysis windowing to be restricted to 364 days following first dose of double-blind IP at visit C1.

Within Part A ACQ-5 assessments will be performed at scheduled clinic visits (according to [Appendix 2: Schedule of Activities](#)) and captured within the subject's eCRF. The ACQ-5 assessments within study Part B, Part C and Part D will be collected on a weekly basis using an eDiary device. Part C data will be summarised weekly relative to the first Part C dose, as shown in the below table.

Domain	Parameter	Target 	Analysis Window 		Analysis Timepoint
			Beginning Timepoint	Ending Timepoint	
eDiary Data	ACQ-5		≥8 days prior to day of first dose		Run-in Period (Not to be summarised)
		Day 1	7 days prior to day of first dose	Date of first dose	Baseline
		Day 8	Day after date of first dose	11 days after date of first dose	Week 1
		Day 15	12 days after date of first dose	18 days after date of first dose	Week 2
		Day 22	19 days after date of first dose	25 days after date of first dose	Week 3
		Day 29	26 days after date of first dose	32 days after date of first dose	Week 4
		Day 36	33 days after date of first dose	39 days after date of first dose	Week 5
		Day 43	40 days after date of first dose	46 days after date of first dose	Week 6
		Day 50	47 days after date of first dose	53 days after date of first dose	Week 7
		Day 57	54 days after date of first dose	60 days after date of first dose	Week 8
		Day 64	61 days after date of first dose	67 days after date of first dose	Week 9
		Day 71	68 days after date of first dose	74 days after date of first dose	Week 10
		Day 78	75 days after date of first dose	81 days after date of first dose	Week 11
		Day 85	82 days after date of first dose	88 days after date of first dose	Week 12
		Day 92	89 days after date of first dose	95 days after date of first dose	Week 13
		Day 99	96 days after date of first dose	102 days after date of first dose	Week 14
		Day 106	103 days after date of first dose	109 days after date of first dose	Week 15
		Day 113	110 days after date of first dose	116 days after date of first dose	Week 16
		Day 120	117 days after date of first dose	123 days after date of first dose	Week 17
Day 127	124 days after date of first dose	130 days after date of first dose	Week 18		
Day 134	131 days after	137 days after	Week 19		

Domain	Parameter	Target 	Analysis Window 		Analysis Timepoint
			Beginning Timepoint	Ending Timepoint	
			date of first dose	date of first dose	
		Day 141	138 days after date of first dose	144 days after date of first dose	Week 20
		Day 148	145 days after date of first dose	151 days after date of first dose	Week 21
		Day 155	152 days after date of first dose	158 days after date of first dose	Week 22
		Day 162	159 days after date of first dose	165 days after date of first dose	Week 23
		Day 169	166 days after date of first dose	172 days after date of first dose	Week 24
		Day 176	173 days after date of first dose	179 days after date of first dose	Week 25
		Day 183	180 days after date of first dose	186 days after date of first dose	Week 26
		Day 190	187 days after date of first dose	193 days after date of first dose	Week 27
		Day 197	194 days after date of first dose	200 days after date of first dose	Week 28
		Day 204	201 days after date of first dose	207 days after date of first dose	Week 29
		Day 211	208 days after date of first dose	214 days after date of first dose	Week 30
		Day 218	215 days after date of first dose	221 days after date of first dose	Week 31
		Day 225	222 days after date of first dose	228 days after date of first dose	Week 32
		Day 232	229 days after date of first dose	235 days after date of first dose	Week 33
		Day 239	236 days after date of first dose	242 days after date of first dose	Week 34
		Day 246	243 days after date of first dose	249 days after date of first dose	Week 35
		Day 253	250 days after date of first dose	256 days after date of first dose	Week 36
		Day 260	257 days after date of first dose	263 days after date of first dose	Week 37
		Day 267	264 days after date of first dose	270 days after date of first dose	Week 38
		Day 274	271 days after date of first dose	277 days after date of first dose	Week 39
		Day 281	278 days after date of first dose	284 days after date of first dose	Week 40
		Day 288	285 days after date of first dose	291 days after date of first dose	Week 41
		Day 295	292 days after date of first dose	298 days after date of first dose	Week 42
		Day 302	299 days after	305 days after	Week 43

Domain	Parameter	Target 	Analysis Window 		Analysis Timepoint
			Beginning Timepoint	Ending Timepoint	
			date of first dose	date of first dose	
		Day 309	306 days after date of first dose	312 days after date of first dose	Week 44
		Day 316	313 days after date of first dose	319 days after date of first dose	Week 45
		Day 323	320 days after date of first dose	326 days after date of first dose	Week 46
		Day 330	327 days after date of first dose	333 days after date of first dose	Week 47
		Day 337	334 days after date of first dose	340 days after date of first dose	Week 48
		Day 344	341 days after date of first dose	347 days after date of first dose	Week 49
		Day 351	348 days after date of first dose	354 days after date of first dose	Week 50
		Day 358	355 days after date of first dose	361 days after date of first dose	Week 51
		Day 365	362 days after date of first dose onwards		Week 52

- [1] If multiple scores are available within analysis window see Section 11.6.1.
- [2] Day of first dose within this table referring to first dose of double-blind IP at visit C1.  
For subjects analysis windowing to be restricted to 364 days following first dose of double-blind IP at visit C1.

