8.3.2.1.1. Guideline for Assessing Multiple Exacerbations

Exacerbations which are separated by less than 7 days will be treated as a continuation of the same exacerbation.

8.3.2.2. eDiary Reporting, Worsening of Asthma and Alerts: Part B, C and D

Subjects should be instructed to bring their eDiary to each Clinic Visit in Part B, Part C and Part D.

The subject will be asked to record the following parameters **daily** in the eDiary from Visit B1 until the completion of Part C or Part D:

- Morning peak flow (best of three), before rescue medication usage (L/min).
- Asthma symptom score over the previous 24-hours using a 6-point scale ([Appendix 7](#))
- Occasions of rescue medication usage over the previous 24-hours
- Frequency of awakening due to asthma symptoms requiring rescue medication use

8.3.2.2.1. eDiary Alerts Indicating Worsening of Asthma

For safety the following alerts, indicative of worsening asthma, will be programmed into the eDiary with instructions to contact the investigator if any of the alert criteria are met.

NOTE: An alert in itself will not qualify as a clinically significant exacerbation:

- Decrease in morning PEF $\geq 30\%$ on at least two of three consecutive days, compared with baseline (last 7 days of run-in Part B)
- A symptom score of 5 for at least two of three consecutive days
- An increase of $\geq 50\%$ in occasions of rescue medication on at least two of three consecutive days, compared with the average use for the previous week.
- Awakening due to asthma symptoms requiring rescue medication use for at least two of three consecutive nights.

Sites should review subject data weekly during Part C through a study specific web portal, and contact subjects for follow-up as appropriate. Additionally, eDiary data will be reviewed at each clinic visit in Parts C and D by the site staff throughout the treatment period to confirm an association between any exacerbation event and eDiary data.

8.3.2.2.2. eDiary Daily Entry: Missed Days of Work or School

Subjects who work for pay or go to school on a regular basis will record in the eDiary any full and part days of missed work or school due to asthma.

8.3.2.2.3. eDiary Weekly Entry: Asthma Control Questionnaire-5 (ACQ-5)

Subjects in Part B, Part C and Part D should complete the ACQ-5 on their eDiary once weekly.

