
 
The estimated means for each treatment group will be calculated from the model using the observed marginal distributions of the sample covariates (OM option in LSMEANS statement).
 
Adjusted absolute means and mean changes from baseline will be presented for each treatment by visit with corresponding standard errors of means. The estimated treatment difference (Mepolizumab – Placebo) will also be presented at each visit with the corresponding 95% confidence intervals and p-values.
 
Plots of LS means change from baseline and 95% confidence intervals from the model will be generated for each treatment by visit.
 

Endpoint / Variables

 
Proportion of patients experiencing a decrease in asthma control, defined as an increase from baseline in ACQ-5 score of <math>\geq 0.5</math> units (ADaM Dataset: ADACQ5)
 
Proportion of subjects with a clinically meaningful worsening of health-related quality of life measurements (SGRQ) at weeks 12, 24, 36 and 52 (defined as subjects who have a clinically relevant increase from baseline of <math>\geq 4</math> units in SGRQ total score) (ADaM Dataset: ADSGRQ)
 

 
See Section 5.2 for further details regarding baseline and change from baseline derivations.
 
See Section 11.6.3 for additional details regarding the ACQ-5 and SGRQ questionnaires.
 
See Section 11.3.5 regarding visit windowing of the ACQ-5 questionnaire.
 

Summary Measure

 
ACQ-5: Odds Ratio (Mepolizumab 100mg SC / Placebo) at weeks 12, 24, 36 and 52
 
SGRQ: Odds Ratio (Mepolizumab 100mg SC / Placebo) at weeks 12, 24, 36 and 52 (Exit Visit/C14)
 

Strategy for Intercurrent (Post-Randomization) Events

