
 
A composite estimand strategy will be applied in the handling of the intercurrent event of discontinuation of double-blind treatment.
 
Subjects will be categorized during the On-treatment (Part C) period according to their questionnaire (ACQ-5 / SGRQ) response. Following treatment discontinuation (end of On-treatment [Part C] phase) subjects will be shown as missing and on analysis included in the least favorable category of increase from baseline of <math>\geq 0.5</math> units or <math>\geq 4</math> units for the ACQ-5 and SGRQ endpoints, respectively.
 
Subjects will be analysed according to the treatment received for more than 50% of injections within Part C (see Section 5.1).
 
All subjects will be considered on-treatment from their first dose of double-blind treatment at visit C1. Subjects who complete Part C will be considered on-treatment up to their Week 52 (Exit Visit/C14) visit date. Subjects who discontinued double-blind treatment will be considered on-treatment until the time of treatment discontinuation. 
 
Questionnaires: see On-treatment (Part C) definition within Section 11.4.3
 
 
 

Model Specification

 
Logistic regression will be used to compare the proportion of patients achieving a 0.5 units / 4 point or greater increase from baseline in ACQ-5 / SGRQ Total Score between treatment groups at each analysis visit (separate models will be used for each analysis visit).
 
Subjects with a missing response at a particular visit will be included in the least favorable category as having a 0.5 units / 4 point or greater increase from baseline in ACQ-5 / SGRQ Total Score in the logistic regression model for the analysis of that visit.
 
Terms fitted in each logistic regression model will include: 
 
Fixed Categorical Covariates: Treatment, Region, Baseline maintenance OCS use [Visit C1]
 
Fixed Continuous Covariates: Baseline Score, Exacerbations in the year prior to randomization [Visit C1] (as an ordinal variable)
 
 
 
 
See Section 5.4.1 for further details around model covariates.

Model Checking & Diagnostics

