**Table 3 Time and Events Table: Fixed Run-In & Double-Blind Treatment Period – Parts B and C**

PARTS B&C Procedures	Fixed Run-in Part B		EW from Part B 	Randomization	Double-Blind Treatment Part C (window is ± 1 week)													IPDISC/EW Visit 
	Visit	B1			B2 	Part B EW	C1	C2	C3	C4	C5	C6	C7	C8	C9	C10	C11	
Week of Study	-4 ± 1	-4 ± 1 		0	4	8	12	16	20	24	28	32	36	40	44	48	52	
Smoking status				X														
Randomization Criteria				X														
Safety Assessments																		
Concomitant Medication	X	X	X	X	X	X	X	X	X	X	X	X	X	X	X	X	X	X
Physical Examination	X		X	X													X	X
Vital Signs	X	X	X	X	X	X	X	X	X	X	X	X	X	X	X	X	X	X
12-lead ECG	X		X							X							X	X
Adverse Events	X	X	X	X	X	X	X	X	X	X	X	X	X	X	X	X	X	X
Laboratory Assessments																		
Haematology	X		X	X	X	X	X	X	X	X	X	X	X	X	X	X	X	X
Chemistry (incl. LFT)	X		X	X						X							X	X
Biomarkers				X	X	X	X	X	X	X							X	X
Pregnancy Test 	U	U	U	U	U	U	U	U	U	U	U	U	U	U	U	U	U	U
Immunogenicity			X														X	X
Efficacy Assessments																		
Subject/Clinician Global Impression Rating				X			X			X			X				X	X
Subject/Clinician Rating of Response to Therapy							X			X			X				X	X
SGRQ				X			X			X			X				X	X

PARTS B&C Procedures	Fixed Run-in Part B		EW from Part B 	Randomization	Double-Blind Treatment Part C (window is ± 1 week)													IPDISC/EW Visit 	
	Visit	B1			B2 	Part B EW	C1	C2	C3	C4	C5	C6	C7	C8	C9	C10	C11		C12
Week of Study	-4 ± 1	-4 ± 1 		0	4	8	12	16	20	24	28	32	36	40	44	48	52		
Exacerbation review	X	X	X	X	X	X	X	X	X	X	X	X	X	X	X	X	X	X	X
Spirometry (pre- and post-albuterol/salbutamol)			X 	X			X			X			X					X	X
Healthcare resource utilization					X	X	X	X	X	X	X	X	X	X	X	X	X	X	X
Review eDiary  (symptoms, rescue use, nocturnal awakenings, PEF, ACQ-5, missed days of work/school)	←																		→
Worksheets/Diary/IP/ eCRF																			
Administer open-label mepolizumab 	X	X																	
Administer double blind study treatment				X 	X	X	X	X	X	X	X	X	X	X	X	X	X		
Dispense albuterol/salbutamol	X	X		X	X	X	X	X	X	X	X	X	X	X	X	X	X		
Collect albuterol/salbutamol	X	X	X	X	X	X	X	X	X	X	X	X	X	X	X	X	X	X	X
Dispense paper diary	X	X		X	X	X	X	X	X	X	X	X	X	X	X	X	X		
Dispense eDiary	X																		
Collect eDiary			X															X	X 

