**11.4.3. Treatment Phases (Visit Based Efficacy and Safety Data)**

Visit based efficacy data, safety data and eDiary data will be classified into treatment phases according to the time of occurrence/assessment relative to the dates of the study treatment and/or the participation of subjects within specific study parts (as dictated by attendance at specific visits) as shown in the table below:

Treatment Phase	Definition
Pre-treatment	Date & time $\leq$ First dose of open-label mepolizumab
On-treatment (Parts A/B)	Subjects who are randomized and receive double-blind treatment: First dose of open-label mepolizumab < Date & time $\leq$ First dose of double-blind treatment Subjects who are not randomized: First dose of open-label mepolizumab < Date & time $\leq$ Earliest of (1) Last dose of open-label mepolizumab + 28 days or (2) Early Withdrawal visit date 
Post-treatment (Parts A/B)	Subjects who are not randomized: Date & time > Earliest of (1) Last dose of open-label mepolizumab + 28 days or (2) Early Withdrawal visit date 
On-treatment (Part C)	Subjects completing study Part C: First dose of double-blind treatment < Date & time $\leq$ C14 (Exit Visit) visit date Subjects discontinuing study treatment/withdrawing early from within Part C: First dose of double-blind treatment < Date & time $\leq$ Earliest of (1) Last dose of double-blind treatment + 28 days or (2) Early Withdrawal / IP Discontinuation visit date Subjects who switch to study Part D: First dose of double-blind treatment < Date & time $\leq$ First dose of open-label mepolizumab within Part D
Post-treatment (Part C)	Subjects completing study Part C: Date & time > C14 (Exit Visit) visit date Subjects discontinuing study treatment/withdrawing early from within Part C: Date & time > Earliest of (1) Last dose of double-blind treatment + 28 days or (2) Early Withdrawal / IP Discontinuation visit date
On-treatment (Part D)	Subjects completing study Part D: First dose of open-label mepolizumab within Part D < Date & time $\leq$ D14 (Exit Visit) visit date Subjects discontinuing study treatment/withdrawing early from within Part D: First dose of open-label mepolizumab within Part D < Date & time $\leq$ Earliest of (1) Last dose of open-label mepolizumab within Part D + 28 days or (2) Early Withdrawal / IP Discontinuation visit date

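### The Week 52 ACQ-5 window conflicts with its own footnote, and under either reading a fully compliant Part C completer can have no Week 52 score and be counted as worsened

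*SAP*

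**What the plan says.** Protocol 8.3.2.2.3 sets the frequency: "Subjects in Part B, Part C and Part D should complete the ACQ-5 on their eDiary once weekly". Neither document ties the entry day to Visit C1.

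The ACQ-5 table in SAP 11.3.5 gives each of Weeks 2 to 51 a 7-day window. Week 51, for example, is days 355 to 361 after first dose. The Week 52 row, with target Day 365, is "362 days after date of first dose onwards" and has no end day. Footnote [2] to the same table says: "For subjects analysis windowing to be restricted to 364 days following first dose of double-blind IP at visit C1".

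SAP 11.4.3 assigns diary data to a treatment phase by date: "Visit based efficacy data, safety data and eDiary data will be classified into treatment phases according to the time of occurrence/assessment". For completers, SAP 7.3.2.1 says: "Subjects who complete Part C will be considered on-treatment up to their Week 52 (Exit Visit/C14) visit date". The Part C schedule (SAP 11.2.1, Table 3) allows visits to move by a week either way.

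The affected analysis is in SAP 7.3.2.1: "ACQ-5: Odds Ratio (Mepolizumab 100mg SC / Placebo) at weeks 12, 24, 36 and 52". Under SAP 11.6.3 a missing score gives a missing responder category. The logistic model in 7.3.2.1 then applies this rule: "Subjects with a missing response at a particular visit will be included in the least favorable category".

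**The concern.** The row and its footnote cannot both be applied as written. One leaves the window open; the other closes it at day 364. Whichever governs, the window can be shorter than the 7-day interval between scores, so whether a subject has a Week 52 value depends on the diary day and the exit date rather than on compliance.

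No other rule recovers the score. SAP 11.6.1 chooses only among values already inside a window. SAP 11.3.3 and 11.3.4 slot early-withdrawal, treatment-discontinuation and unscheduled data, not a completer's routine weekly entry. There is no carry-forward rule. The SGRQ has no equivalent loss, because SAP 11.3.2 keeps clinic assessments made outside the visit window.

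At stake is the Week 52 ACQ-5 responder comparison. The composite strategy there is stated for discontinuation of double-blind treatment. Here it would also catch people who finished treatment, attended exit and missed no weekly entry.

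**Working it through.** Days below are days after the first double-blind dose, so study Day 365 is day 364.

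**Window widths.** The rows for Weeks 2 to 51 follow the rule day 7w − 2 to day 7w + 4. For w = 51 this gives 355 to 361, as in the table. For w = 52 it gives a start of 7 × 52 − 2 = 362, again as in the table, and would give an end of 368. With the cap, days 362, 363 and 364 remain: 3 days instead of 7. Without it, the window is 362 to the Exit Visit.

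**Example that holds under both readings.** Entries on days 358 and 365, exit on day 364. Day 358 falls in Week 51. Day 365 is after exit, so it is not on-treatment (and is also past the cap). There is no Week 52 score.

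**All cases.** Take exact weekly entries on each of the 7 possible diary days, with exit on each in-window day (364 ± 7 = 357 to 371). Diary days with no Week 52 score:

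| Exit day | Cap applies | Cap ignored |
|---|---|---|
| 357–361 | 7 of 7 | 7 of 7 |
| 362 | 6 of 7 | 6 of 7 |
| 363 | 5 of 7 | 5 of 7 |
| 364 | 4 of 7 | 4 of 7 |
| 365 | 4 of 7 | 3 of 7 |
| 366 | 4 of 7 | 2 of 7 |
| 367 | 4 of 7 | 1 of 7 |
| 368–371 | 4 of 7 | 0 of 7 |

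Over the 7 × 15 = 105 combinations, a score is present in 27 with the cap and 49 without it. These are counts of cases, not expected frequencies. At Weeks 12 (82–88), 24 (166–172) and 36 (250–256), all 7 diary days give a score.

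**Scale, as illustration only.** Protocol 5.3 anticipates about 120 Part C completers. If the cap applies, diary days are evenly spread and exit is on day 364 or later, 4/7 = 57% are affected: 120 × 4/7 = 68.6, about 69.

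**Effect on the odds ratio.** Assume 150 per arm, with 30% (mepolizumab) and 50% (placebo) of completers truly worsened. Let c be the proportion completing, p the proportion worsened among completers and m the proportion of completers with no Week 52 score. Non-completers already count as worsened, so the analysed proportion is (1 − c) + c × [p + (1 − p) × m].

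- c = 0.4 in both arms, m = 0: 0.720 v 0.800, OR 0.64 (95% CI 0.38–1.10), SE of log OR 0.27.
- c = 0.4 in both arms, m = 4/7: 0.880 v 0.914, OR 0.69 (0.32–1.46), SE 0.39.
- c = 0.5 v 0.3, m = 0: 0.650 v 0.850, OR 0.33 (0.19–0.57), SE 0.29.
- c = 0.5 v 0.3, m = 4/7: 0.850 v 0.936, OR 0.39 (0.18–0.86), SE 0.40.

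Neither conclusion changes. The interval widens and the odds ratio moves slightly toward 1.

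**The case against.** The best defence is that the row's open end was intended and the footnote was carried over. The same sentence stands under the daily-diary table in SAP 11.3.5, whose last row repeats the 364-day limit; the ACQ-5 row does not. A reader might infer that the window is 3 days however the text is read. The documents do not support that: if *onwards* governs, the window runs to the Exit Visit and no diary day misses for exits from day 368. The defence does not remove the gap, because exits up to day 367 still leave some diary days without a score.

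A second objection is that entries may cluster on C1 anniversaries. The diary is dispensed at B1, nominally four weeks before C1, and every ACQ-5 target is an anniversary. An entry on day 364 with exit on day 364 or later is captured, so the loss could be zero. This stands as a limit on the size. The ±1 week visit windows weaken it, and exit before day 364 loses even an anniversary entry.

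Third, the impact is small. About 180 of 300 subjects are not expected to complete Part C, and those who discontinue are already counted as worsened. The endpoint has no multiplicity control, and the window rule is the same in both arms. All of this stands and sets the severity.

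**Conclusion.** The row and footnote conflict, and under either reading the rules can classify a fully compliant completer as worsened at Week 52. Severity is minor: the misclassification affects one of four timepoints of one 'other' endpoint. The Week 52 ACQ-5 mean difference only loses data.

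Two stronger inferences are not supported. One is that 57% of completers, about 69, will be misclassified. That figure needs the cap to apply, evenly spread diary days and exit on day 364 or later; the documents fix none of these, and the possible range is 0 to 100%. The other is that the main results are at risk. The primary endpoint does not use ACQ-5, and the secondary time to loss of asthma control does not count a missing score as an event.

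The day counts assume exact 7-day spacing and need no other assumption. The odds-ratio figures rest on the assumed completion and worsening rates.

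**What to change.** Before unblinding, amend SAP 11.3.5 for ACQ-5:

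- Drop the 364-day cap.
- For Part C completers, define Week 52 as the on-treatment score closest to Day 365. Start the window at the earlier of day 362 or 6 days before the Exit Visit, but no earlier than day 351 (6 days before the earliest in-window exit, day 357). End it on the Exit Visit date.
- Leave the Week 50 and 51 windows and weekly summaries as they are. A score may also serve as Week 52, but must not enter one repeated-measures model twice.
- Keep the least-favorable rule for scores still missing, and report by arm how many completers have none at Week 52.

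For exits on days 357 to 371 this window is 7 to 10 days wide and captures a score in 105 of 105 combinations. Removing the cap alone captures 49, and only 3 of 7 diary days when exit is on day 364.

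The cost is SAP wording and window programming. With exit on day 357 the score can be as early as day 351, which is 364 − 351 = 13 days before target. With exit on day 364 or later it lies between 6 days before and 4 days after. In 56 of the 105 combinations the chosen score comes from the Week 50 or 51 range, so it can appear twice in the weekly descriptive tables. Exits before day 357 can still leave no score and would show in the reported count.
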